Appendix 2. Data Derivation Details

Appendix 2.1. Definition and Use of Visit Windows in Reporting

The following table provides the windows categorizing dated assessments under nominal visits for the purpose of reporting.

Nominal Visit	Visit window for clinical-based assessment	Visit window for imaging-based assessment
Baseline	Day 1	date of the first MRI or ultrasound for organ volumes at Screening visit; date of the first assessment around Day 1 (Baseline visit) for other imaging-based measurement.
Month 3	12 weeks -7 days < Visit date ¹ – Day 1 +1 <= 12 weeks + 7 days	NA
Month 6	26 weeks -7 days < Visit date – Day 1 +1 <= 26 weeks + 7 days	26 weeks -42 days < Assessment date ² – Baseline assessment date +1 <= 26 weeks +42 days
Month 9	38 weeks -7 days < Visit date – Day 1 +1 <= 38 weeks + 7 days	NA
Month 12	52 weeks -7 days < Visit date – Day 1 +1 <= 52 weeks + 7 days	52 weeks -42 days < Assessment date ² – Baseline assessment date +1 <= 52 weeks +42 days

¹ visit date is the date collected on the top of the pages for each visit.

² assessment date for organ volume (ie, spleen and liver) and skeletal assessment (eg, skeletal age and bone mineral density) are collected as the “Date of assessment” on the corresponding eCRF modules.

Handling Missing Dates

Missing visit dates will be handled according to Pfizer CDISC data standard for imputation. Missing day in assessment date will be imputed as the first day of each month. If the month is missing for assessment date, the visit date collected at the same visit will be used.

Handling Multiple Observations in the Same Visit Window

If there are multiple observations in one participant falling into one single visit window, the worst assessment will be used for summary. The imaging-based assessment will less likely have multiple observations in the same visit window. The clinical lab-based test, such as hemoglobin and platelet, may have this situation. Since increase from baseline in hemoglobin and platelet indicating clinical improvement, then the least increase from baseline or most decrease from baseline will be considered as the worst assessment in handling multiple observations in the same visit window.

The definition of the worst assessment for some of the biomarkers or measurements may involve other considerations. For example, the worst assessment for bone age estimation needs to be compared to the chronological age. For tanner stage and testis volume, it will be assessed at individual case though lower categorical number or lower volume usually indicates as the worse assessment. In such cases and any parameters not specified above, the definition of the worst assessment will be decided case by case and will be documented in the programming document, such as analysis datasets specification.

Appendix 2.2. Endpoint Derivations

Not applicable.

Appendix 2.3. Definition of Protocol Deviations That Relate to Statistical Analyses/Populations

Not applicable.

Appendix 3. Data Set Descriptions

Not applicable.

Appendix 4. Statistical Methodology Details

1. Sample code for Wilcoxon signed rank test:

```

data one;
  input id $ pre post;
  label pre='Baseline' post='Mon12';
  cards;
1    8.74  4.22
2    6.77
4    1.34  1.95
5    4.52  3.76
6    6.72  5.85
7    2.37  2.74
8    3.69  2.93
9    4.55  3.62
10   17.12 16.84
11   14.93 18.07
;run;
data two;
  set one;
  pctch=((post-pre)/pre)*100;
  adjpctch=pctch + 20;  ** for primary efficacy endpoint **;
run;

** Wilcoxon signed rank test for primary efficacy endpoint with decision
criteria;
proc univariate data=two;
  var adjpctch;
  output out=rankpct SIGNRANK=statistics PROBS=p median=median;
run;

** Wilcoxon signed rank test for secondary efficacy endpoints;
proc univariate data=two;
  var pctch;
  output out=rankpct SIGNRANK=statistics PROBS=p median=median;
run;

```

2. Sample code for Clopper-Pearson exact test and CI for the responder rate:

```

data three;
  input status $ count;
  cards;
  respond 8
  nonresp 1;
run;
proc freq data=three;
  table status/binomial (exact p=0.5) alpha=0.05;
  weight count;
run;

```

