4.3 Overview of Clinical Data

4.3.1 Study PB-06-001 in Adult GD Patients

Study PB-06-001 was a Phase 3, multicenter (11 centers worldwide), double-blind trial in which 32 adult patients with Type 1 GD randomly received either 30 units/kg or 60 units/kg of taliglucerase alfa intravenously every 2 weeks for 38 weeks (20 infusions). At the end of the study, eligible patients were offered enrollment in an open-label extension study (PB-06-003).

The primary efficacy analysis demonstrated that taliglucerase alfa treatment significantly reduced spleen volume from screening to Month 9 (taliglucerase alfa 30 units/kg, 26.91%, p<0.0001; taliglucerase alfa 60 units/kg, 38.01%, p<0.0001) and Month 6 (taliglucerase alfa 30 units/kg, 22.21%, p<0.0001; taliglucerase alfa 60 units/kg, 29.94%, p<0.0001).

The secondary efficacy analysis demonstrated that taliglucerase alfa treatment significantly increased hemoglobin level from baseline to Month 9 (taliglucerase alfa 30 units/kg, 1.6 g/dL, p<0.0001; taliglucerase alfa 60 units/kg, 2.2 g/dL, p<0.0001). A significant reduction in liver volume from screening was also observed in both taliglucerase alfa dose groups at the end of the study (taliglucerase alfa 30 units/kg, 10.48%, p=0.0041; taliglucerase alfa 60 units/kg, 11.11%, p<0.0001). In addition, a significant increase in platelet count from baseline was observed in the 60 units/kg dose group at Month 9 (41,494/mm³, p=0.0031) and an increase in platelet count at Month 9 was also observed for the taliglucerase alfa 30 units/kg dose group (11,427/mm³, p=0.0460). Improvements were also observed at the Month 6 visit.

Overall, 23 patients experienced 137 adverse events (AEs) (12 in the 30 units/kg had 65 AEs and 11 in the 60 units/kg had 72 AEs). Eight patients (3 in the 30 units/kg group and 5 in the 60 units/kg group) experienced 28 events that were considered by the respective investigators to be treatment-related. Of the treatment-related events, none were seen in more than one patient in each group. All AEs were mild or moderate in intensity and the majority of the events resolved by the end of the study. No deaths or serious adverse events (SAEs) occurred during the study. Two patients (1 per dose group) discontinued from the study due to a hypersensitivity reaction.

Pharmacokinetic (PK) analyses showed no tendency for accumulation or change in PK parameters with repeated doses of taliglucerase alfa.

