The following data are the changes [median (Q1, Q3)] in clinical parameters from baseline to Month 12 for the 60 units/kg dose group (n=5): spleen volume decreased from 18.4 (14.2, 35.1) MN to 11.0 (8.3, 14.5) MN; hemoglobin increased from 11.1 (9.2, 11.3) g/dL to 11.7 (11.5, 12.9) g/dL; liver volume decreased from 2.1 (2.0, 2.3) MN to 1.6 (1.5, 1.9) MN; platelet count increased from 80,000 (79,000, 87,000)/mm³ to 131,000 (119,000, 215,000)/mm³.

Nine pediatric patients in the 12-month clinical trial continued blinded treatment with ELELYSO in an extension trial for a total treatment duration of 24 months. The following data are the changes [median (Q1, Q3)] in clinical parameters from baseline to Month 24 for the 60 units/kg dose group (n=5): spleen volume decreased by 19.0 (8.3, 41.2) MN; hemoglobin increased by 2.5 (1.9, 3.0) g/dL; liver volume decreased by 0.8 (0.6, 1.1) MN; and platelet count increased by 76,000 (67,000, 100,000)/mm³.

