2.1.1. Primary Estimand(s)

The primary estimand of this study uses the treatment policy strategy and estimates the effect for all participants are treated and regardless of whether an intercurrent event occurs. It includes the following 4 attributes:

- Population: All patients who suffer from the Type 3 GD as defined by the inclusion and exclusion criteria, and who have received at least one complete dose (or partial dose if adverse events prevent completing infusion dose);
- Variable: Percent change from baseline to Month 12 in spleen volume expressed in MN (Multiples of Normal) and measured by MRI (Magnetic Resonance Imaging);
- Intercurrent event: All data after an intercurrent event (discontinuation of treatment, discontinuation of study, etc), if collected, will be included;
- Population-level summary: median percent change from baseline to Month 12 and p-value from the Wilcoxon signed ranks test.

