5. GENERAL METHODOLOGY AND CONVENTIONS

5.1. Hypotheses and Decision Rules

For the primary efficacy endpoint, a Wilcoxon signed rank test at 2-sided significance level of 0.05 will be applied to test the null hypothesis that the median percent change from baseline to Month 12 in spleen volume MN is equal to -20%. The corresponding p-value will be reported.

The primary null hypothesis is:

$$H_0: \lambda = -20\%$$

and the primary alternative hypotheses are:

$$H_{a1}: \lambda < -20\% \text{ and } H_{a2}: \lambda > -20\%,$$

where λ is the common median of the observed percent difference from the paired data.

Taliglucerase alfa will be considered efficacious with respect to the spleen volume MN, if the median percent change from baseline to Month 12 is significantly less than -20% (or the median percent reduction is greater than 20%) at the 2-sided 0.05 level, ie, p-value from Wilcoxon signed rank test less than 0.05.

For the secondary efficacy endpoints, such as hemoglobin, platelet counts and Lyso-Gb1, the same Wilcoxon signed rank test will be applied for the percent change from baseline to Month 12. No adjustment for multiple comparisons will be made. Though hemoglobin, platelet counts, chitotriosidase and Lyso-Gb1 will be collected at Month 3, 6 and 9 as well, changes from baseline to Months 3, 6 and 9 will be descriptively summarized only.

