5.2.2. Analyses for Continuous Endpoints

The Wilcoxon signed rank test will be performed for the percent change from baseline to Month 12 in primary and secondary efficacy endpoints due to the possible skewed distribution for the efficacy data.

The rank with positive and negative signs will be assigned to the percent difference (D_i) between baseline and Month 12 values. D_i are a random variable, which are mutually independent from each participant and have the same median. All the zero differences are ignored in the analysis. The Wilcoxon signed rank test inference is based on permutational distribution of its test statistics. This test will be implemented and exact p-values will be produced via SAS Proc Univariate. The Proc Univariate excludes missing values for an analysis variable before calculating statistics. The sample code is provided in [Appendix 4](#).

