6. ANALYSES AND SUMMARIES

6.1. Primary Endpoint

6.1.1. Main Analysis

- Estimand strategy: Treatment policy strategy for percent change from baseline to Month 12 in spleen volume MN measured by MRI.
- Analysis set: FAS (defined in [Section 4](#)). All participants assigned to study drug and received at least 1 complete dose of taliglucerase alfa (or partial dose if adverse events prevent completing infusion dose) will be included.
- Analysis methodology: Percent change from baseline to Month 12 will be analyzed using Wilcoxon signed rank test detailed in [Section 5.2.2](#). In order to judge whether this primary efficacy endpoint meets the 20% reduction from baseline, a 20% shift will be added on the percent change from baseline for each participant in the analysis set before the procedure of Proc Univariate ([Appendix 4](#)).

- Intercurrent events and missing data: Data after study drug discontinuation will be included. Missing values will be imputed using LOCF and other methods specified in [Section 5.3](#) and be included in calculating percent change from baseline.
- Summary of statistical comparison: The 2-sided p-value from the exact inference for Wilcoxon signed rank statistics for comparing Month 12 to baseline value, as well as the median percent change from baseline, will be presented and used to judge whether efficacious criteria is met. The n, minimum and maximum for the observed percent change from baseline will be presented together as well.
- Descriptive summary including n, mean, SD, median, minimum, and maximum for absolute value, change from baseline and percent change from baseline in spleen volume and spleen volume MN measured by MRI at each visit will be presented.

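### The SAP's sample code for the primary endpoint saves the median of percent change plus 20, not the median percent change that the SAP reports and uses to judge efficacy

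*SAP*

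**What the plan says.** SAP Section 3 defines percent change as post-baseline minus baseline, over baseline, times 100, with no shift. The primary estimand in SAP 2.1.1 is summarized as follows: "Population-level summary: median percent change from baseline to Month 12 and p-value from the Wilcoxon signed ranks test". SAP 5.1 declares the drug efficacious on spleen volume "if the median percent change from baseline to Month 12 is significantly less than -20" percent at the 2-sided 0.05 level. SAP 6.1.1 says that the exact p-value, "as well as the median percent change from baseline, will be presented and used to judge whether efficacious criteria is met". Protocol 10.3.4 likewise asks for the median percent change and its p-value.

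On implementation, SAP 5.2.2 says "This test will be implemented and exact p-values will be produced via SAS Proc Univariate" and points to Appendix 4. SAP 6.1.1 adds that each participant's value is shifted by 20 before the procedure, so that the test addresses a 20% reduction, and it also refers to Appendix 4.

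Appendix 4 computes `pctch`, then "adjpctch=pctch + 20". The call labeled for the primary endpoint has `var adjpctch` and the statement "output out=rankpct SIGNRANK=statistics PROBS=p median=median". The call labeled for secondary endpoints has `var pctch` and the identical output statement, with the same data set name.

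**The concern.** In PROC UNIVARIATE the saved median belongs to the variable named in the VAR statement. For the primary endpoint that is the shifted variable, so the value called `median` is not the quantity in the estimand or in the reporting rule. The unshifted median is saved only by the secondary call, whose p-value tests against 0. Because both calls write to `rankpct`, the second replaces the first if they are run in sequence. At no point does `rankpct` hold the required pair: the p-value against -20% and the unshifted median.

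The median matters to the decision because the test is two-sided. A small p-value alone does not say whether the reduction is larger or smaller than 20%. A reader who takes direction from the saved median must compare it with 0, yet the criterion in SAP 5.1 invites comparison with -20. Nothing in the saved data set signals the change of scale.

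**Working it through.** The SAP prints no output for its sample code, so there is no stated figure to reproduce. The check is to carry out the Appendix 4 steps on the data listed there.

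**Step 1. Percent change and shifted value.** `pctch = (post - pre)/pre × 100`; `adjpctch = pctch + 20`. Subject 2 has no printed Month 12 value and is excluded.

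| id | pre | post | pctch | adjpctch |
|---|---|---|---|---|
| 1 | 8.74 | 4.22 | -51.72 | -31.72 |
| 4 | 1.34 | 1.95 | 45.52 | 65.52 |
| 5 | 4.52 | 3.76 | -16.81 | 3.19 |
| 6 | 6.72 | 5.85 | -12.95 | 7.05 |
| 7 | 2.37 | 2.74 | 15.61 | 35.61 |
| 8 | 3.69 | 2.93 | -20.60 | -0.60 |
| 9 | 4.55 | 3.62 | -20.44 | -0.44 |
| 10 | 17.12 | 16.84 | -1.64 | 18.36 |
| 11 | 14.93 | 18.07 | 21.03 | 41.03 |

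**Step 2. Medians (fifth of nine ordered values).** `pctch`: -12.95. `adjpctch`: +7.05. Difference: 7.05 - (-12.95) = 20.00. This is general: adding a constant to every value moves the median by that constant.

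**Step 3. Exact signed rank tests by full enumeration.**
- `adjpctch` (null -20%): the positive ranks are 3, 4, 5, 7, 8 and 9, sum 36; S = 36 - 22.5 = 13.5; two-sided p = 0.1289.
- `pctch` (null 0): the positive ranks are 3, 7 and 8, sum 18; S = 18 - 22.5 = -4.5; two-sided p = 0.6523.

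**Step 4. What is saved and what is wanted.**

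| | p | median |
|---|---|---|
| Primary call saves | 0.129 (against -20%) | +7.05 |
| Secondary call saves | 0.652 (against 0) | -12.95 |
| SAP text requires | 0.129 (against -20%) | -12.95 |

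**Step 5. The short row.** If the listing is read literally, so that subject 2's missing value is filled with the 4 that starts the next line, subject 2's percent change is (4 - 6.77)/6.77 = -40.92% and subject 4 drops out. The medians become -16.81 and +3.19, again 20.00 apart.

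**Step 6. Where the offset would mislead.** A saved value between -20 and 0 corresponds to a true median between -40% and -20%. Two earlier results in the Protocol show whether that range is realistic:
- Protocol 4.3.1, adults at Month 9: "taliglucerase alfa 60 units/kg, 38.01%, p<0.0001". A change of -38.01 would be saved as -38.01 + 20 = -18.01.
- Protocol Appendix 1, Clinical Studies, pediatric 60 units/kg group at Month 12: "spleen volume decreased from 18.4 (14.2, 35.1) MN to 11.0 (8.3, 14.5) MN". (11.0 - 18.4)/18.4 = -40.2%, which would be saved as about -20.2.

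These are illustrations only. The adult figure is for Type 1 disease at Month 9 and is not described as a median; the pediatric figure is a ratio of two medians, because individual percent changes are not given.

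**The case against.** The strongest reply is that the plan itself is sound. The text states the unshifted median consistently, SAP 6.1.1 discloses the shift and its purpose, and the variable name and code comment mark it as adjusted. The listing is sample code on invented data, cited in SAP 5.2.2 for the test and its exact p-values, and both are right. It does not save the n, minimum and maximum that 6.1.1 also wants, so it was never a complete source for the primary table. Direction can be read from the sign of the saved signed rank statistic, or from the shifted median against 0. The descriptive summary in 6.1.1 would show a median 20 points lower and reveal the mismatch. Of the two illustrations, the pediatric one is saved as -20.2, still just below -20, so it would not look like a miss.

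All of this stands, and it limits the consequence. It does not remove the fault. Sections 5.2.2 and 6.1.1 both send the programmer to this listing, and its output statement asks for the median explicitly. Run as written, it yields a value on the wrong scale for a quantity that 6.1.1 uses in the efficacy judgment. The safeguards depend on someone noticing the discrepancy.

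**Conclusion.** The point holds. The median saved by the primary-endpoint code is 20 percentage points above the median percent change, whatever the data, and neither call produces the pair of results that SAP 6.1.1 requires. The signed rank test and its p-value against -20% are correct as coded, as is the SAP text.

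The size of the error is certain; its effect on the trial is conditional. It matters only if the saved value is reported as the median percent change or compared with -20%. It would then understate the effect, and a true median between -40% and -20% would appear to miss the criterion. It cannot create a false claim of efficacy. It should be corrected before the code is used, but it is a modest fault because the p-value is unaffected and the slip can be detected.

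**What to change.** In SAP Appendix 4, keep the signed rank statistic and p-value from `adjpctch` but take the primary median from `pctch`. Equivalently, drop the shifted variable and run `pctch` with `MU0=-20`, which gives the same test and the unshifted median in one call. If the second route is chosen, align the sentence on the shift in 6.1.1. Write the primary and secondary results to differently named data sets.

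Two small repairs belong in the same edit of Appendix 4:
- The PROC FREQ responder code names no level. For its example of 8 responders in 9, the Clopper-Pearson interval is 51.8% to 99.7% for responders but 0.3% to 48.2% for non-responders, and SAP 6.1.2 judges the lower bound against 50%. Add `level='respond'`.
- Put the semicolon that closes that data block on its own line.

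The cost is a few lines of sample code. The hypothesis, test, alpha, sample size and analysis sets do not change.

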Appendix 5. List of Abbreviations

Abbreviation	Term
Abs	absolute
AE	adverse event
TEAE	Treatment emergent adverse event
BOCF	baseline observation carried forward
BP	blood pressure
CDISC	Clinical Data Interchange Standards Consortium
CDC	Center of Disease Control and Prevention
CI	confidence interval
CRF	case report form
CSR	clinical study report
ECG	electrocardiogram
FAS	full analysis set
FDA	Food and Drug Administration (United States)
ICD	informed consent document
ICH	International Council for Harmonisation
Lyso-Gb1	Lyso-glucosylsphingosine
LOCF	last observation carried forward
MedDRA	Medical Dictionary for Regulatory Activities
MN	Multiples of Normal
MRI	Magnetic Resonance Imaging
mSST	modified Severity Scoring Tool
N/A	not applicable
PP	per-protocol
PPAS	per-protocol analysis set
PT	preferred term
QTc	corrected QT
QTcF	corrected QT (Fridericia method)
SAE	serious adverse event
SAP	statistical analysis plan
SD	standard deviation
SOP	standard operating procedure
SUSAR	suspected unexpected serious adverse reaction
TA	therapeutic area
ULN	upper limit of normal
VAS	visual analog scale
WHO	World Health Organization
WHODD	World Health Organization Drug Dictionary
